Postmenopausal Pessary Users: Estrogen versus Trimosan

NCT03943823

Version Date: 09/28/2015

IRB Protocol

Protocol Title: Postmenopausal Pessary Users: Estrogen versus Trimosan

Principal investigator: [name]

Co-investigators: [name], [name], [name]

Study Coordinator: [name]

Population: Postmenopausal female new pessary users

Number of sites: Harris Health Clinics. Ben Taub Clinics. UT Houston Clinics

Study Duration: 6 months – 1 yr

Subject Duration: 3 months

General information:

Pelvic organ prolapse is seen in close to 96% of postmenopausal women (1). A pessary, which is a device placed into the vagina to support the prolapsing vaginal walls or to provide urinary continence, is commonly used to treat pelvic organ prolapse.

A common complication noted in pessary users is bothersome vaginal discharge. Vaginal discharge complication rates vary in different publications, ranging from 2.5% to 25% (2, 3). This complication may not cause pessary users to discontinue use (4); however, from clinical experience, it can be a source of embarrassment for the patient and a deterrent for family members to aid in self-care.

Little is known about the vaginal discharge in pessary users. In studies of vaginal discharge in pessary users, the symptomatic vaginal discharge is commonly attributable to bacterial vaginosis (5).

It is uncertain how vaginal pH is primarily established, but multiple factors are thought to contribute to establishing the acidic vaginal pH. Lactobacilli bacteria produce lactic acid, which is the primary acid in vaginal in normal vaginal secretions. The vaginal mucosa is also known to be an important source of lactic acid (12--6). While pH is known to alter the vaginal microbial environment, it has been shown that a pessary itself does not alter the microbial environment. (9)

The microbial composition between postmenopausal non pessary and pessary users have shown to be essentially similar (9).

Background Information:

Current popular creams used as an adjunct to pessary use are estrogen and trimo-san. Vaginally applied estrogen promotes epithelial cell growth and cellular maturation, decreases vaginal pH to premenopausal levels, and decreases severity of vulvovaginal symptoms (7)

Trimosan is a vaginal gel, with a pH of 4, marketed to help restore and maintain the normal vaginal acidity and coats the walls of the vagina with a lubricating film that helps reduce odor causing bacteria (8). There are not yet any published trials regarding Trimo-San's efficacy.

Bacterial vaginosis occurs in a setting of vaginal pH > 4.5, with peak adherence to vaginal mucosa occurring at pH 5 -6 (6).

There are previous papers which suggest that acidifying gels have been able to treat BV and prevent recurrence compared to placebo in its ability to acidify the vaginal pH. (Successful treatment of bacterial vaginosis with a policarbophil-carbopol acidic vaginal gel; recurrent bacterial vaginosis: the use of maintenance acidic vaginal gel following treatment). Given these suggestive findings, it goes to follow that Trimo-san may also be effective in decreasing pH and bacterial vaginosis infections.

In one study, vaginal pH of 6.0 to 7.5 is strongly suggestive of menopause (13). While it is known that estrogen can reduce vaginal pH and that Trimo-san may potentially do the same, these creams have never been studied in the context of pessary users.

Objectives:

Study hypothesis: In postmenopausal pessary users, estrogen users will have a more acidic pH, less complaints of vaginal discharge/odor, and decreased rates of bacterial vaginosis, than trimosan users.

Primary objective: vaginal pH with both treatment arms, as measured by pH test strips

Secondary objective: to see difference of patient satisfaction between treatment arms as measured by an unvalidated vaginal symptoms questionnaire.

Tertiary objective: rate of bacterial vaginosis infection (to be diagnosed either by gram stain (Nugent Score) or BV Affirm.

Study Design:

- 1) Randomized controlled
- 2) Study duration: 1 year 3 years.
- 3) Subject duration: 3 months
- 4) Assessment of efficacy: Cost savings, future increase in compliance as less medication may be needed overall, possible decrease in bacterial vaginosis infection
- 5) Assessment of safety: Estrogen Side effects abnormal vaginal bleeding, nausea, breast tenderness, bloating. Otherwise, low risk study.

Study Population:

6) Number of subjects to be enrolled? 34. 17 in each arm. Power 80%. P value: 0.05 P value 0.5. Power 80%. Sample size calculated with the expectation that estrogen will drop vaginal pH to 5.5 and Trimosan will decrease vaginal pH to 4.5.

- Recruitment: Will recruit 44 patients (assuming 15% non enrollment, and 15% drop out) This study will be open to all clinic patients at Harris Health (LBJ, Aldine, BT Clinics), UT Houston clinics (Memorial Hermann, Sugarland, Memorial City),
- 8) All participants will read and sign The Certificate of Informed Consent when they arrive at the designated testing site, prior to their participation in the research procedure. After the participants have finished their participation in the study, or once they have decided to withdraw from the study, they will be given a verbal and written debriefing statement.
- 9) Inclusion:
 - Postmenopausal female pessary user (ring with support pessaries only) 18 years and older. Postmenopausal defined as: 1) amenorrhea for a year 2) 3 months after surgical bilateral salpingo-oophorectomy
 - Is a new pessary user, or has not had a pessary for a year
- 10) Exclusion:
 - Pregnancy
 - o Persistent Bacterial Vaginosis infection in the first two clinic encounters
 - Currently on hormone replacement therapy
 - Previously on hormone replacement therapy in the past 6 months
 - o Currently on antibiotics
 - Patients with existing vaginal erosions/ulcerations

Study Procedures:

Estrogen Treatment Arm: Will use either Premarin or Estrace cream (dependent on patient's insurance). Premarin 1 gram every night for the first 7 days, then 0.5 grams twice weekly. Estrace cream – 2 grams daily for first 7 days, then 1 gram twice-weekly.

Trimosan Treatment Arm: ½ applicator for three times a week for 1st week, then ½ applicator for 2 times a week.

The procedures are different because of funding/resources differences at Harris Health Clinics versus UT clinics. At Harris Health, they can be fitted for a pessary, but they must then take a prescription to an outside pharmacy in order to buy their personal pessary, and must come back to have it placed. At UT clinics, they have a ready stock of pessaries that the patients may purchase at the time of their fitting.

For Harris Health and BT Clinics:

1st encounter - Clinic visit to fit pessary from kit, pessary will be ordered, vaginal pH collected, vaginal gram stain collected, pt will fill out questionnaire, and be randomized to a treatment arm.

2nd encounter – Clinic visit to have their own pessary inserted, and be advised treatment according to which treatment arm they were randomized to.

3rd encounter – Clinic visit in 2 weeks after pessary fitting to evaluate vaginal tissue and symptoms.

4th encounter – Telephone call (6 weeks after personal pessary fitting) – to remind patient of their next visit and compliance with treatment.

5th encounter - 3 month clinic visit – vaginal pH to be collected, vaginal gram stain, will fill out questionnaire. Exit process explained and standard of care for pessary users will be continued.

For UT clinics:

1st encounter: Patients will be fitted for a pessary, and their own pessary will be placed, consented, fill out questionnaire, vaginal pH collected, BV affirm collected, randomized to a treatment arm, cream will be prescribed.

2nd encounter: Clinic visit in 2 weeks after pessary fitting to evaluate vaginal tissue and symptoms.

3rd encounter – telephone call – 6 weeks after initial pessary fitting to remind patients of next visit and compliance with creams

4th encounter – 3 month clinic visit: vaginal pH to be collected, BV affirm to be collected, will fill out questionnaire. Exit process explained and standard of care for pessary users will be continued.

Data and Safety Monitoring:

- 11) No adverse events expected
- 12) Plans for reporting unanticipated problems: ***
- 13) Safety monitoring plan periodic review by research team

Statistics: Level of significance p 0.5

Ethics

- IRB approval will be sought from CPHS.

The PI will see the patient. If the PI thinks that the patient may qualify for a study, she will communicate basic information to the patient and will inform the patient that the research coordinator will talk to her. The research coordinator will gather the pertinent information and will talk to the patient. If the patient agrees to hear about the study, the patient will be moved to a private room, if applicable. The PI will explain the consent form in the patient's native language provided that language is either English or Spanish. Other languages will require a consent form translated into the patient's native language. The PI will explain the study through the consent form page by page and will give the patient plenty of time to read the form and ask questions. If the patient agrees to participate then both the patient and the PI will sign the ICF and a copy will be given to the patient. Then in accordance with the protocol, the INC/EXC criteria will be revised and the screening test will be scheduled at the patient's convenience.

Data handling and record keeping

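### No primary analysis of vaginal pH is named; pre-specify ANCOVA of 3-month pH on arm, adjusted for first-encounter pH and clinic system

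*Combined protocol and SAP*

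**What the plan says.** Under Objectives, the endpoint is "Primary objective: vaginal pH with both treatment arms, as measured by pH test strips". No time point, summary measure or method is attached. The whole Statistics entry is "Statistics: Level of significance p 0.5".

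Two other places hint at the intended contrast. The study hypothesis is that "estrogen users will have a more acidic pH". Study Population, item 6, has "Sample size calculated with the expectation that estrogen will drop vaginal pH to 5.5 and Trimosan will decrease vaginal pH to 4.5", with 17 women per arm and 80% power. Both speak of the pH level reached; neither gives an expected baseline or an expected change. Item 6 also prints two significance levels side by side: "P value: 0.05 P value 0.5. Power 80"%.

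Under Study Procedures, pH is taken at the first encounter and at the 3-month visit in both clinic systems:

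- Harris Health/BT, first encounter: "vaginal pH collected, vaginal gram stain collected, pt will fill out questionnaire, and be randomized to a treatment arm". Treatment starts only at the second encounter, where the woman will "be advised treatment according to which treatment arm they were randomized to".
- UT, first encounter: "vaginal pH collected, BV affirm collected, randomized to a treatment arm, cream will be prescribed". Here the woman's own pessary is listed as placed before pH is taken. At Harris Health/BT her own pessary is inserted one encounter after pH is taken.

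**The concern.** A single continuous endpoint measured at baseline and at follow-up can be compared as a final value, as a change, or as a final value adjusted for baseline. The plan commits to none of these. Two things are at stake.

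The first is precision. If the natural reading (final value) is followed, a baseline measurement that is already paid for does no work. In a trial of 34 women, that could matter.

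The second is credibility. If the analysis is chosen after results are seen by arm, the nominal error rate no longer holds, and a reader of the published result could not tell whether that happened.

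**Working it through.** **Inputs.** From the protocol: 17 per arm; expected pH 5.5 and 4.5, so an absolute difference of 1.0; power 80%; alpha printed as both 0.05 and 0.5. Not in the protocol, so assumed: two-sided testing, alpha 0.05 for the main figures, SD of 3-month pH 1.0, normal data. The baseline-to-3-month correlation r is shown over 0 to 0.7.

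**The plan's own figure.** No SD is given, so 17 per arm cannot be reproduced from the plan alone. Working backwards with a two-sample t-test at two-sided 0.05, 17 per arm and 80% power imply an SD of 1.009. At SD 1.0 the noncentrality is 1.0 / (1.0 × √(2/17)) = 1.0 / 0.343 = 2.92 on 32 df, and power is 80.7%. So 17 per arm fits an unadjusted final-value comparison if the SD is about 1.0.

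**ANCOVA on baseline pH.** Residual SD = SD × √(1 − r²), that is 1.000, 0.954, 0.866 and 0.714 at r = 0, 0.3, 0.5 and 0.7, with 31 df. Power is averaged over chance baseline imbalance between arms. Leaving that imbalance out gives slightly flattering values (80.6, 84.1, 90.3 and 97.7%).

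**Change score.** SD of the change = SD × √(2(1 − r)) when the two visits have equal SDs, with 32 df.

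| r | Final value | ANCOVA | Change score (equal SDs) |
|---|---|---|---|
| 0 | 80.7% | 79.4% | 51.6% |
| 0.3 | 80.7% | 83.0% | 66.6% |
| 0.5 | 80.7% | 89.4% | 80.7% |
| 0.7 | 80.7% | 97.3% | 95.4% |

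ANCOVA breaks even with the unadjusted test at r = 0.18. Its largest loss is 80.7 − 79.4 = 1.3 points.

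**Other SDs.** At SD 0.75, unadjusted power is 96.5% and ANCOVA gives 95.9, 97.2, 98.9 and 99.9%. At SD 1.25 the figures are 61.9% and then 60.4, 64.5, 72.8 and 87.5%, so the largest loss is 1.5 points.

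**The other printed alpha.** At two-sided 0.5, 17 per arm and 80% power imply an SD of about 1.9–2.0. At SD 1.92, unadjusted power is 81.3% and ANCOVA gives 80.8, 82.5, 86.0 and 92.4%. The pattern is the same.

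**Worst-case false positives.** In simulated null trials at nominal 5%, each analysis alone holds 4.9–5.1%. The rates below count a trial as positive if any permitted analysis gives p < 0.05.

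- Final value or ANCOVA: about 5.7, 6.5, 7.1–7.3 and 8.1–8.4% at r = 0, 0.3, 0.5 and 0.7. The ratio of baseline to 3-month SD has no effect here, because rescaling a covariate leaves ANCOVA unchanged.
- Change score added: 8.7, 9.1, 9.6 and 10.0% with equal SDs; about 7.1–8.7% at an SD ratio of 0.4; up to 11.2% at a ratio of 1.3 with r = 0.7.

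All figures are two-sided, so they do not depend on which arm is expected to end lower. The hypothesis and the sample-size sentence disagree on that; it is a separate matter to reconcile.

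**The case against.** The strongest reply is that the choice is less open than the silence suggests. The hypothesis and the sample-size sentence both describe levels reached, so a final-value comparison is the natural reading. It is valid, and simply pre-specifying it would close the choice. This largely stands. What remains is that a planning assumption is not an analysis statement, that neither sentence rules baseline adjustment in or out, and that the unadjusted test is less precise once r exceeds about 0.18.

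A reader might infer that the gap nearly doubles the false-positive rate whatever the correlation. The documents do not support that. It requires treating the change score as a live option, which is the weakest reading of the text, and it depends on the SD ratio. The protocol's Background gives pH 6.0 to 7.5 as suggestive of menopause. If baseline values were spread evenly over that range (an assumption), their SD would be 1.5/√12 = 0.43, well below an assumed 3-month SD of 1.0. The three-way ceiling would then be nearer 7–9%. The poor change-score power in the table is likewise the equal-SD case: at SD ratios of 0.3–0.5 it is 71–77% at r = 0 and 83–84% at r = 0.3.

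A reader might also infer bias in the treatment comparison. Nothing shows that; randomisation protects the unadjusted contrast.

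Two further objections stand in part. First-encounter pH is taken at a different point in pessary fitting in the two clinic systems, so clinic system belongs in the model. And the calculations treat test-strip readings as continuous and normal, which was not examined.

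**Conclusion.** The point holds as a recommended improvement, not as a flaw in validity. The plan names no primary analysis. Its wording leans toward achieved 3-month pH compared without adjustment, and it makes no use of a baseline it already collects.

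At SD 1.0 and alpha 0.05, adjusting for baseline pH changes power from about 81% to between 79% (r = 0) and 97% (r = 0.7). These figures adjust for baseline pH only. SD, correlation, sidedness and normality are all assumptions, so the size of the gain is uncertain. The small size of the possible loss is much less so.

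Closing the post-hoc choice is the secondary benefit. The figures of about 6–8% and 7–11% are ceilings reached only if the most favourable result is always reported; they are not expected rates.

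First-encounter pH is a legitimate covariate because it is listed before study treatment in both systems. That it also precedes allocation is shown only by the order of the lists.

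**What to change.** In Statistics, before any outcome is seen by arm, state that:

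- the primary analysis is ANCOVA of 3-month vaginal pH on treatment arm, adjusted for first-encounter pH and clinic system (Harris Health/BT or UT);
- the result is reported as an adjusted mean difference with a 95% confidence interval, tested at the significance level the sponsor confirms, since 0.05 and 0.5 are both printed;
- an unadjusted final-value comparison is a sensitivity analysis, and the raw change score is not primary.

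In both first-encounter procedures, add that pH is recorded before the arm is assigned. While editing, it would be sensible to state sidedness, the analysis set and the handling of a missing 3-month pH, given the 15% drop-out the plan assumes.

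The cost is a few sentences in Statistics and one clause in each procedure, with no new data, visits or patients. If baseline pH proves uninformative, the loss is about 1.3 points of power at SD 1.0 (1.5 at SD 1.25), plus one further degree of freedom for clinic system.

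### Nothing in the plan keeps the person reading the 3-month pH strip unaware of treatment arm, although pH is the only outcome with a sample-size basis

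*Combined protocol and SAP*

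**What the plan says.** Under Objectives, the primary objective is "vaginal pH with both treatment arms, as measured by pH test strips". The protocol gives no strip type, increment, reading procedure, duplicate reading or named reader.

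Under Study Design, the design is given only as "Randomized controlled". Blinding or masking of patient, clinician or reader is not mentioned anywhere.

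The two treatments differ in form, measure and schedule. Under Study Procedures, the estrogen arm uses one of two creams, dosed in grams, with a 7-day initial phase. Background Information describes the comparator: "Trimosan is a vaginal gel, with a pH of 4". Its regimen under Study Procedures is "½ applicator for three times a week for 1st week, then ½ applicator for 2 times a week". No placebo or matched packaging is described.

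Clinic staff learn the arm. At Harris Health and BT, patients at the 2nd encounter are to "be advised treatment according to which treatment arm they were randomized to". At the UT clinics, the 1st encounter has the patient "randomized to a treatment arm, cream will be prescribed". Both site groups then have a 2-week clinic visit, a 6-week telephone call that covers compliance, and a 3-month visit at which pH is collected.

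The study hypothesis is that "estrogen users will have a more acidic pH" than Trimosan users. The sample-size line under Study Population expects a pH of 5.5 on estrogen and 4.5 on Trimosan.

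**The concern.** If the strip is matched by eye to a colour scale, a reading that falls between two blocks leaves room for judgement. A reader who knows the arm, and expects something of it, can resolve such readings one way more often in one arm than in the other. That produces a systematic difference between arms. Recruiting more patients would not remove it, and since nothing would record who read the strip or what they knew, the analysis could not examine it afterwards.

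The stake is the primary comparison. pH is the only outcome for which the plan gives a sample-size basis, and with 17 per arm a shift of a few tenths of a pH unit is not negligible beside the differences the test can detect.

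**Working it through.** **1. The plan's own figure.** The inputs stated under Study Population are 17 per arm, 80% power and a difference of 5.5 − 4.5 = 1.0. No SD is given, so the 34 cannot be reproduced. It can be solved backwards from n = 2·SD²·(z₀.₉₇₅ + z₀.₈₀)²/δ²:

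SD = 1.0 × √(17/2) / (1.960 + 0.842) = 2.915 / 2.802 = 1.04 (1.01 with the t distribution), at two-sided 0.05.

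An SD near 1.0 is therefore consistent with the plan, but it is not stated there. The protocol also prints 0.5 as the significance level, under Study Population and under Statistics. At two-sided 0.5 the implied SD would be 1.92. What follows uses 0.05.

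**2. Which reading is exposed.** At both site groups the 1st encounter lists pH collection before randomization. If that order is followed, the baseline reader cannot know the arm. The 3-month reading comes after arm-specific advice or prescription, a 2-week visit and a compliance call. That leaves one exposed reading per patient.

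**3. Direction.** The hypothesis puts estrogen lower and the sample-size line puts Trimosan lower. A reader could take either expectation from the protocol, so no sign can be given to the bias.

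**4. Smallest significant difference.** SE = SD × √(2/17) = 0.343 × SD. With 32 degrees of freedom the critical t is 2.037, so at SD 1.0 the threshold is 2.037 × 0.343 = 0.70 pH.

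**5. Effect of an assumed shift when there is no true difference.** The noncentrality parameter is shift / SE, and the rejection probability comes from the noncentral t with 32 degrees of freedom, two-sided 0.05.

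| Assumed SD | Shift 0.25: noncentrality | False-positive rate | Shift 0.5: noncentrality | False-positive rate |
|---|---|---|---|---|
| 1.25 | 0.58 | 8.7% | 1.17 | 20.5% |
| 1.0 | 0.73 | 10.9% | 1.46 | 29.3% |
| 0.75 | 0.97 | 15.6% | 1.94 | 47.0% |

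The shifts are assumptions. If the colour scale had steps of 0.5 pH, moving half of one arm's readings by one step would give 0.5 × 0.5 = 0.25, and moving all of them would give 0.5. The second case is an extreme.

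**6. Effect when the true difference is 1.0 (SD 1.0).** Power is 81% without a shift. A shift of 0.25 changes it to 56% if it works against the true difference, or to 94% if it works with it.

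**The case against.** Much of the mechanism is inferred. The protocol says only that strips are used. It does not mention a colour chart, reading by eye, or who reads. That the products look different is inferred from cream against gel and from the different measures and schedules. A reader might also infer that the people who prescribe the cream read the strip, or that the trial is declared open-label. The documents say neither: the reader is unnamed, and masking is simply not addressed.

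A reader might further infer that the team leans towards estrogen and will bias the result that way. The sample-size line points the other way, so this is not supported.

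The error rates rest on stacked assumptions: the size of the shift, its consistency within one arm, and the SD. They show sensitivity and are no evidence that such a shift will occur.

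Full masking at no staffing cost is not shown to be possible. The documents place no uninvolved staff member at the 3-month visit. A fixed order of steps cannot make someone forget an arm they already know, and the protocol describes Trimosan as leaving a film on the vaginal walls, so product may be visible at examination.

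All of this stands as a limit on how strongly the point can be put. It does not answer the gap itself: the plan does not say who takes the primary reading, how, or with what knowledge of the allocation.

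**Conclusion.** The point holds in a limited form. As written, the plan leaves the 3-month reading of its primary outcome open to reader expectation and describes no safeguard. Baseline readings are largely protected by the listed order of steps.

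The possible size is material but not known. Over SDs of 0.75 to 1.25, a between-arm shift of 0.25 pH would raise a nominal 5% error rate to between 8.7% and 15.6%, and a shift of 0.5 to between 20.5% and 47.0%. These figures assume 17 per arm, a two-sided 0.05 test and a visually read strip. They do not show that bias will occur, and the documents do not support assigning it a direction. The hypothesis and the sample-size expectation contradict each other and must be reconciled in their own right.

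The safeguard is cheap, so it should be added.

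**What to change.** Add to the 3-month visit, at both site groups:

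- The strip is read against one fixed colour chart, following a short written procedure.
- The value is written down and signed before the allocation or medical record is opened, and before cream use or symptoms are discussed.
- Where existing staffing allows, the reader is a team member who neither prescribed nor advised the treatment.
- The form records who read the strip and whether that person knew the arm. A sensitivity analysis can then compare or restrict to readings by unaware readers.

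Separately, reconcile the expected direction in the study hypothesis with that in the sample-size line.

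The cost is a fixed order of steps at one visit and an added entry on the data form. Patients need not be masked, and treatment does not change. The downside is that masking is partial: a reader may remember the arm or see product at the examination. The report should say so. With 17 per arm, a sensitivity analysis restricted to unaware readers may also be imprecise.

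### Bacterial vaginosis is measured by a different assay in each clinic system but stated as one rate, with no stratification, by-system analysis or common definition of a positive result

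*Combined protocol and SAP*

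**What the plan says.** In the combined protocol and SAP, the Objectives section gives the tertiary objective as a single BV rate, "to be diagnosed either by gram stain (Nugent Score) or BV Affirm". The study hypothesis in the same section expects estrogen users to have "decreased rates of bacterial vaginosis, than trimosan users", so a comparison of BV between arms is intended.

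Study Procedures settles which assay each woman gets:

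- **Harris Health and BT clinics.** At the first encounter: "vaginal gram stain collected, pt will fill out questionnaire, and be randomized to a treatment arm". At the 3-month visit: "vaginal pH to be collected, vaginal gram stain, will fill out questionnaire".
- **UT clinics.** At the first encounter: "BV affirm collected, randomized to a treatment arm, cream will be prescribed". BV Affirm is collected again at the 3-month visit.

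The same section attributes the differing procedures to the resources of the two systems. Study Design says only that the trial is randomised and controlled. Study Population sets 34 women, 17 per arm, on the basis of expected pH. The Statistics section consists of a significance level. No randomisation method, BV test, site term or Nugent cut-off appears anywhere.

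**The concern.** Two different tests need not call the same proportion of women positive. If the results go into one rate per arm, part of any difference between arms can come from how many women in each arm had each test. With 17 women per arm and no stated stratification by clinic system, the arms can differ noticeably in their mix of assays.

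The second problem needs no assumed figures. A Nugent score becomes a rate only once a cut-off is chosen, and none is given. No rule says when a Gram-stain positive and a BV Affirm positive count as the same event. The pooled proportion is therefore a blend of two case definitions, weighted by whatever the clinics happen to recruit. The exclusion for persistent BV would likewise rest on a different test in each system.

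**Working it through.** The plan states no BV rate, sample size or power, so there is no figure of its own to reproduce.

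**Inputs from the document.** 34 women, 17 per arm (Study Population); assay fixed by clinic system, and randomisation to either arm within both systems (Study Procedures).

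**Assumed inputs.** 17 women from each system; a difference in positivity between the assays (the gap) of 10 to 20 percentage points. The documents give neither.

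**1. Expected shift.** Let K be the number of Gram-stain women in one arm. Under unstratified 17:17 allocation, K is hypergeometric (34 women, 17 Gram-stain, 17 drawn), with mean 8.5. The difference between arms in Gram-stain share is D = (2K − 17)/17, which has mean 0. With no treatment effect, the assay contribution to the arm difference is gap × D, so its expectation is 0.

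**2. Typical shift.** SD(K) = √(17 × 0.5 × 0.5 × 17/33) = 1.48, so SD(D) = 2 × 1.48/17 = 0.174. Multiplied by a gap of 10 to 20 points, this is 1.7 to 3.5 points. With 10 women in one system and 24 in the other, SD(D) is 0.159, so the result depends little on the assumed split.

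**3. Less favourable splits.**

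| Split of Gram-stain women | Probability of this or worse | D | Shift, gap 10 | Shift, gap 20 |
|---|---|---|---|---|
| 11:6 | 16.9% | 5/17 = 0.294 | 2.9 points | 5.9 points |
| 12:5 | 3.8% | 7/17 = 0.412 | 4.1 points | 8.2 points |

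One woman in an arm of 17 is 1/17 = 5.9 points, so the largest shift shown is about 1.4 BV cases.

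**4. Type I error.** 20,000 trials per scenario were simulated with no treatment effect, 17 women per system and unstratified allocation, using the pooled two-sided 5% chi-square test. It rejected in 4.5% of trials with equal positivity (30% and 30%), and in 4.7% to 4.8% with gaps of 10, 20 and 30 points centred on 30%. There is no inflation above 5%.

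**5. Meaning of the pooled rate.** Assume true BV rates of 30% and 10%. An assay with sensitivity 0.8 and specificity 0.95 shows 27.5% and 12.5%, a difference of 15 points. One with sensitivity 0.6 and specificity 0.95 shows 21.5% and 10.5%, a difference of 11 points. These accuracies are illustrations. They show that the observed effect can depend on the assay even when the arms are perfectly balanced.

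**6. Effect of stratifying.** Lists balanced within system would give splits of about 9:8, leaving a crude shift of at most 1/17 × gap, or 0.6 to 1.2 points. Comparing arms within system removes that as well. In simulation at nominal 5%, the exact test stratified by system rejected in about 3% of null trials, against about 2% for pooled Fisher. For 30% against 10%, its power was about 23%, against about 19%.

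**The case against.** A reader might infer that treatment is confounded with assay, or that the pooled test would give too many false positives. The documents do not support either. Assay follows clinic system, each system randomises to both arms, and each woman has the same test at baseline and at 3 months. Steps 1 and 4 show zero expected bias and no inflation of type I error. What remains is ordinary chance imbalance in one factor, which the error rate of the test already covers.

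A reader might also infer that the plan prescribes a crude pooled comparison. It does not: it describes no BV analysis at all, and the supportable statement is that stratification and by-system analysis are not specified. This is one instance of a wider silence, since no test is named for any endpoint.

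The effect is also small beside sampling error. At an illustrative BV rate of 30%, the standard error of the arm difference is √(2 × 0.3 × 0.7/17) = 15.7 points, against a typical assay shift of 1.7 to 3.5. BV is a tertiary outcome, and power for 30% against 10% is only about 30% by the usual normal approximation, even with a perfect assay. No choice of test makes this a decisive comparison.

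All of this stands, and it limits the point to a minor one. It does not answer the missing definition of a positive result, which randomisation cannot supply. Nor does it remove the case for a change that costs almost nothing.

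**Conclusion.** The point holds in a limited form. The plan states one BV rate from two assays fixed by clinic system, and it specifies no stratification, by-system analysis or common positivity definition. The consequences are possible chance imbalance of assay between arms and a pooled rate without a clear meaning. Systematic bias and excess false positives are not among them.

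The sizes in steps 2 and 3 rest on the assumed even split of women between systems and the assumed gap of 10 to 20 points; they scale in proportion to the gap. The missing definition rests on no assumption. This is a cheap improvement of low priority, because BV is tertiary and the trial was not sized for it.

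**What to change.** - Stratify randomisation by clinic system (Harris Health/BT, UT), with allocation balanced within each. If randomisation has begun, stratify the analysis only.
- State what counts as BV-positive for each assay, including the Nugent cut-off.
- Report 3-month BV by arm within each system, and compare arms with an exact test stratified by system (exact Mantel-Haenszel).

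**Cost.** Two randomisation lists instead of one and a few lines of analysis text; no extra specimens or visits. The exact stratified test remains conservative, at about 3% for a nominal 5%, though less so than pooled Fisher. Within-system rates will be imprecise: with about 8 or 9 women per arm in each system, one woman moves a rate by 11 to 12.5 points (1/9 to 1/8). They should be presented as descriptive. Stratifying removes the effect of assay imbalance but does not make the two assays equivalent, so the separate definitions and by-system reporting are needed as well.
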